6 ASSESSMENT SCHEDULE

Subjects will be enrolled for duration of 6 months including the screening visit

- Screening visit 1 (Treatment initiation)
- Visit 2: after 1st month, follow-up 1
- Visit 3: after 2nd month, follow-up 2
- Visit 4: after 3rd month, follow-up 3
- Visit 5: after 4th month, follow-up 4
- Visit 6: after 5th month, follow-up 5

7 Determination of Sample Size:

As the primary objective is to assess the efficacy of Ursoplus[®] capsules (UDCA 250mg & Silymarin 140mg) versus UDCA alone versus Placebo among Egyptian NASH Patients in reduction of total serum bilirubin, and based on the previous study of [the hepatoprotective effect of Silymarin and UDCA in CHC patients][i], which have been conducted on 40 patients; 10 patients received silymarin, 10 patients received UDCA, 10 patients received Silymarin + UDCA and 10 patients received Placebo.

And this study showed that:

The 12 weeks treatment period of Placebo did not show significant improvement regarding T Bilirubin levels $1.6 \pm 1.0 \text{ Vs.} 1.8 \pm 0.7$, p=0.166

A statistically significant improvement in mean \pm SD serum T bilirubin levels 1.3 \pm 0.5 vs. 1.2 \pm 0.5, p = 0.016 was obtained with 500mg/day UDCA therapy

In addition, the mean \pm SD; T. bilirubin levels for the combined therapy group (Silymarin + UDCA) decreased significantly 1.4 \pm 0.1 vs. 1.2 \pm 0.3, p= 0.022

Given that a researcher has the null hypothesis that $\mu=\mu 0$ and alternative hypothesis that $\mu=\mu 1\neq \mu 0$, and that the population variance is known as $\sigma 2$. Also, he knows that he wants to reject the null hypothesis at a significance level of α which gives a corresponding Z score, called it $Z\alpha/2$. Therefore, the power function will be

```
P\{Z > Z\alpha/2 \text{ or } Z < -Z\alpha/2|\mu 1\} = 1-\Phi[Z\alpha/2-(\mu 1-\mu 0)/(\sigma/n)]+\Phi[-Z\alpha/2-(\mu 1-\mu 0)/(\sigma/n)].
```

So, the following parameters are used to calculate the expected sample of the study:

Design: F tests - ANOVA: Fixed effects, omnibus, one-way, Analysis: A priori: Compute required sample size

• Input:

o Effect size f = 0.2124591 o α err prob = 0.05 o Power (1- β err prob) = 0.863 o Number of groups = 3

[figure not shown]
Output:

[figure not shown]
Non-centrality parameter λ = 12.1874947
 Critical F = 3.0295971
 Numerator df = 2
 Denominator df = 267

Denominator df
 Total sample size
 Actual power
 267
 270
 0.8697572

- Confidence level 95% (α error = 5%)
- Study Power = 87%
- Sample Size = 270 Subjects (1:1:1)
- Drop out = 10% (27 subjects)
- Total number of patients: 297 subjects.
- Ursoplus Sample Size =99 subjects

- Placebo Sample Size = 99 subjects
- UDCA Sample Size = 99 subjects

8 Randomization:

Randomization is done using Stratified random sampling according to Vibration-controlled transient elastography in screening visit:

Group with non-cirrhosis (group1), F0, F1 and F2.

Group with advanced fibrosis and cirrhosis (group2), F3 and F4.

Subjects will be randomized into the 3 treatment groups with a balanced ratio of 1:1:1 by Data Management department (DM) of CRO (Nagy Research). The number of patients of the three treatment groups will be balanced (ratio 1:1:1). (99 Ursoplus[®]: 99 UDCA: 99 Placebo). Figure 1 shows Stratified Random Sample

[figure not shown]

Figure 1: Stratified Random Sampling

9 Blinding

NA, as study is open label.

10 Code-Breaking:

NA

11 Data Analysis:

11.1 Test for Normality, reliability and validity:

Normality, reliability and validity tests are to be done before the main data analysis, to choose the appropriate statistics and significant tests that will be used.

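### The power, effect size and target power printed in SAP section 7 cannot come from one calculation: the printed f at N = 270 gives 88.5% power, not 87%

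*SAP*

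**What the plan says.** SAP section 7 (Determination of Sample Size) names the method as "Design: F tests - ANOVA: Fixed effects, omnibus, one-way, Analysis: A priori: Compute required sample size". The inputs are "Effect size f = 0.2124591", "α err prob = 0.05", "Power (1- β err prob) = 0.863" and "Number of groups = 3". The outputs are "Non-centrality parameter λ = 12.1874947", "Critical F = 3.0295971", numerator df 2, denominator df 267, a total of 270 and an actual power of 0.8697572. The summary lines then give "Study Power = 87" per cent, 270 subjects in a 1:1:1 ratio, 10% dropout (27 subjects) and 297 in total.

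The section cites an earlier study with total bilirubin means before and after 12 weeks: placebo 1.6 to 1.8, UDCA 1.3 to 1.2, and the combination 1.4 to 1.2. The SDs quoted with these means run from 0.1 to 1.0. The section does not show how f was obtained from these figures, and it states no common SD.

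**The concern.** For a one-way ANOVA, once f, alpha, the number of groups and N are fixed, the noncentrality, critical F and power are all determined. Two of these three outputs match the printed inputs and the third does not, so the power line appears to come from another run. The section is also labelled as a search for the required N, yet 270 is not the N that the printed target requires.

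Section 7 is the only justification for 270 evaluable and 297 enrolled patients. With inconsistent entries, a reader cannot say which effect size the 87% refers to, and the power quoted for the trial is not that of the design printed beside it.

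**Working it through.** **Inputs (SAP section 7):** f = 0.2124591; alpha = 0.05; k = 3 groups; N = 270; target power 0.863; printed power 0.8697572.

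**1. Reproduce the plan's intermediate figures.**
- lambda = f² × N = 0.2124591² × 270 = 0.0451389 × 270 = 12.18749. Printed: 12.1874947. Match.
- Degrees of freedom: k − 1 = 2 and N − k = 267. Match.
- Critical F = 95th percentile of F(2, 267) = 3.029597. Printed: 3.0295971. Match.

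**2. Power from those same figures.**
- Power = P[F(2, 267; lambda = 12.1874947) > 3.0295971] = 0.88457, against 0.8697572 printed.
- Difference: 0.88457 − 0.86976 = 0.0148, or 1.5 points.
- A simulation of the noncentral F ratio with 4 million draws gives 0.8850. A large-sample chi-square version gives 0.8882. Changing alpha does not rescue the printed figure: 0.025 gives 0.820 and 0.10 gives 0.935.

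**3. Which effect size gives the printed power?**
- Solving P[F(2, 267; lambda) > 3.0295971] = 0.8697572 gives lambda = 11.6667.
- f = √(11.6667 / 270) = 0.20787.

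**4. Does the target of 0.863 lead to 270 for either effect size?** The entries are power in equal arms.

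| Effect size | Largest N below target | Smallest N reaching 0.863 | Power at 270 |
|---|---|---|---|
| f = 0.2124591 (printed) | 252: 0.8605 | 255: 0.8648 | 0.8846 |
| f = 0.20787 (from the printed power) | 264: 0.8617 | 267: 0.8658 | 0.8698 |

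Neither search stops at 270. More generally, if 270 were the smallest equal-arm total reaching 0.863, power at 267 would have to be below 0.863. The effect size that gives exactly 0.863 at 267 gives only 0.8670 at 270, which is below the printed 0.8698. So no single f reconciles the target 0.863, N = 270 and actual power 0.8698. This step needs no assumption about means or SDs.

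**5. Possible origin of the two effect sizes (inference only).** Take f as the SD of the group means (divisor 3) over a common SD.
- Cited mean changes +0.2, −0.1, −0.2: SD of means 0.16997; 0.16997 / 0.80 = 0.21246, the printed f.
- Cited baseline means 1.6, 1.3, 1.4: SD of means 0.12472; 0.12472 / 0.60 = 0.20787, the f behind the printed power.

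Neither 0.80 nor 0.60 is stated in the SAP.

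**The case against.** The strongest reply is that the gap is small and harmless. It is 1.5 points, inside the 2 points often allowed when a power figure is re-derived. For the printed f the plan understates its power. The 270 patients exceed what either effect size needs for 0.863, and no analysis or patient number depends on the power line. All of this stands, and it is why the point is minor. It does not remove the mismatch. A tolerance covers rounding or a different method; here the method is the same, and lambda and critical F agree to about seven figures.

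The output lines are also disordered in the PDF text. That does not explain the gap: the 87% summary line repeats the printed power, and 0.8697572 is what 270 patients give for another effect size.

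Two stronger readings are tempting. A reader might infer that 87% is the wrong figure. The documents do not support that: if f = 0.20787 was intended, 87% is right and the printed f and lambda are wrong. A reader might also infer that the trial was powered on baseline differences, or that its SD was 0.80. Both are back-solved from figures that happen to fit. The SAP states neither, so they are questions for the sponsor.

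The missing derivation of f would be a gap even if the power line were correct. It should not raise the weight given to this arithmetic error.

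**Conclusion.** The inconsistency is certain, and its effect is small. As printed, f, alpha, groups and N give power 0.8846. The printed 0.8697572 belongs to f = 0.20787 (lambda 11.667). The target 0.863 leads to 255 or 267 patients in equal arms, not 270.

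If the printed f is right, power is understated by about 1.5 points and 270 exceeds the 255 needed by 15. If the 87% run is right, the printed f is too high by about 2% (0.2124591 / 0.20787 = 1.022). The documents do not show which entry is wrong.

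These results rest only on the printed inputs and the exact noncentral F distribution; the sources suggested for the two effect sizes are inference. Severity: minor.

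**What to change.** In SAP section 7, state the group means and common SD from which f was derived, rerun the calculation once, and print all inputs and outputs from that run.

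- If f = 0.2124591 stands: change the actual power to 0.8846 and the study power to 88.5%.
- If the 87% run was intended: correct f to 0.20787 and lambda to 11.667, and leave the power as printed.
- In either case: replace the input power of 0.863 with the target actually used.
- Confirm that f reflects the treatment changes in bilirubin and not the baseline values.

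On this ground N stays at 270 evaluable and 297 enrolled. The cost is SAP wording and one rerun; the design and the analyses do not change.

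### The 10% drop-out allowance is taken on the 270 evaluable patients, not the 297 enrolled, so 297 covers 9.1% drop-out; the effect on power is negligible

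*SAP*

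**What the plan says.** SAP section 7 (Determination of Sample Size) sets out a power calculation labelled "Design: F tests - ANOVA: Fixed effects, omnibus, one-way", with "Number of groups = 3", "α err prob = 0.05", "Effect size f = 0.2124591" and "Power (1- β err prob) = 0.863" as inputs. The printed output is a total of 270, denominator degrees of freedom 267, a noncentrality parameter of 12.1874947, a critical F of 3.0295971 and an actual power of 0.8697572, summarised as 87%.

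The section then steps from that number to enrolment in three lines: "Sample Size = 270 Subjects (1:1:1", "Drop out = 10% (27 subjects" and "Total number of patients: 297 subjects". Enrolment is split as 99 per arm, and the protocol's case report form repeats 297 and 99 per arm.

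SAP section 11.2 restricts every efficacy analysis to patients who complete the trial without a protocol violation. Neither document defines the drop-out rate in any other way, for example as a percentage of completers.

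**The concern.** A drop-out rate describes what happens to the patients who are enrolled. Here the 10% is applied to the number meant to remain after drop-out, so the allowance is slightly too small for the rate that labels it. Because drop-outs contribute nothing to the efficacy test under section 11.2, the printed degrees of freedom and noncentrality parameter describe the trial only if 270 patients are left to analyse.

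What is at stake is the accuracy of a planning statement. The SAP tells its reader that 297 enrolled can absorb 10% drop-out and still deliver 270, and it cannot. The size of the gap decides how much this matters.

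**Working it through.** **Inputs**, all from SAP section 7: 270 evaluable patients, 10% drop-out given as 27, 297 enrolled, three groups, alpha 0.05, f = 0.2124591. Section 11.2 supplies the reason to treat 270 as the number after drop-out.

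**Step 1. Reproduce the plan's enrolment figure.**
- 0.10 × 270 = 27, and 270 + 27 = 297. This is n × (1 + d), and it matches the SAP exactly.

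**Step 2. Apply the rate to those enrolled.**
- Drop-out that leaves 270: 27 / 297 = 0.0909, or 9.1%.
- Loss at 10%: 0.10 × 297 = 29.7.
- Patients remaining: 0.90 × 297 = 267.3, about 267 (89 per arm instead of 90).
- Enrolment needed for 270 to remain at 10%: n / (1 − d) = 270 / 0.90 = 300.

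The difference is 3 patients in total, 1 per arm, whether counted as evaluable (270 against 267) or enrolled (300 against 297).

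**Step 3. Effect on power.** For a one-way omnibus F test, the noncentrality parameter is λ = f² × N, with 2 and N − 3 degrees of freedom. Power is the probability that a noncentral F variable exceeds the central-F critical value at alpha 0.05.

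| Evaluable N | Denominator df | λ = 0.2124591² × N | Critical F | Power |
|---|---|---|---|---|
| 270 | 267 | 12.1875 | 3.0296 | 0.8846 |
| 267 | 264 | 12.0521 | 3.0300 | 0.8808 |

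The row for 270 reproduces the SAP's printed λ and critical F. Its power does not equal the printed 0.8697572; the gap is 0.8846 − 0.8698 = 0.0148, about 1.5 percentage points. That is a separate issue in the SAP's calculation. A simulation of 100,000 trials at each size gave 0.8847 for 270 and 0.8812 for 267, in line with the table.

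**Step 4. Compare with the plan's targets.** Going from 270 to 267 costs 0.8846 − 0.8808 = 0.0038, about 0.4 percentage points. The result, 0.8808, is above the stated 87% and above the 0.863 input. With the printed f, the smallest balanced total that reaches 0.863 is 255 (power 0.8648), which is 12 fewer than 267.

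**The case against.** The best defence is that the three lines agree on their own terms. The SAP shows its base by printing 27 beside the 10%, and 270 plus 27 is 297. Read as a 10% over-recruitment margin, nothing is miscalculated, and adding n × d is a shortcut that some planners use. It is fair to say that the SAP's sum is internally consistent and that the disagreement is over which inflation formula to use. But the line is labelled as drop-out and not as a margin, no other base is defined, and the efficacy analysis keeps completers only. As a statement about drop-out, 10% is not what 297 covers.

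The second objection is that the gap is trivial, and this stands. One patient per arm is less than other features of the plan will move the analysed numbers: protocol violators are also removed under section 11.2, and the table shells for Tables 3 to 9 compare treatments within each fibrosis group.

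A reader might infer that the trial falls below its planned power at 10% drop-out. The documents do not support that: with the SAP's own f, power at 267 is 0.881, above 87%. A lower figure appears only if f is back-solved to force the printed power of 0.8697572 at 270. That gives f = 0.20787 and a power of 0.8658 at 267. But this f implies λ = 0.20787² × 270 = 11.667, which contradicts the printed 12.1874947, so 0.8658 should not be used.

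**Conclusion.** The point holds as a small arithmetic correction. The allowance in SAP section 7 covers 9.1% drop-out among the 297 enrolled, not 10%, and a 10% loss leaves about 267 evaluable patients rather than 270. The cost is 3 patients and about 0.4 percentage points of power, and the planned power is still met.

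This rests on two assumptions: that drop-out is a fraction of patients enrolled, which is the ordinary meaning and is not contradicted in the documents, and that 270 is the number to be analysed, which follows from section 11.2. The power figures also assume the printed f and an unstratified three-group F test with equal arms, as section 7 does. They take no account of patients lost to protocol violations, which would come on top of drop-out. The mismatch between the printed f and the printed power is a different matter, and this point does not depend on how it is resolved.

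**What to change.** Keep 297 enrolled and correct the drop-out line in SAP section 7 in one of two ways:

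- State the allowance as 9.1%, being 27 of 297 enrolled, leaving 270 evaluable; or
- Keep 10% and state that about 267 evaluable patients (89 per arm) are expected, with denominator degrees of freedom 264, noncentrality parameter 12.05, and power recomputed at 267 from the printed f (0.881).

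Section 11.3 foresees a final SAP before database lock in which differences are documented, so the correction can go there. No change to enrolment, randomisation or analysis is needed. The only cost is a slightly lower stated drop-out tolerance under the first option, or a slightly lower stated evaluable number under the second. If the second is chosen, the recomputed power will be higher than the printed 0.8697572 because of the separate mismatch noted above. The SAP should say so, so that the rise is not read as a gain from the drop-out correction.

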Patients must only be identified by the subject identification ID (Center number, Patient number

Adverse Event Log/Concomitant Medication Log

If additional pages of adverse event and / or concomitant medication log are required, please make a photocopy of a blank adverse Event log / concomitant medication log and complete the information. The original page will be sent to data management and a photocopy retained at Minapharm and investigator site

Dates

- 1- All dates are to be reported in the format DD/MMM/YYYY
- 2- The month is to be reported as the first three characters of the month, e.g. 01/AUG/2012 the month abbreviations are as follows:

January	=	Jan	May	=	May	September	=	Sep
February	=	Feb	June	=	Jun	October	=	Oct
March	=	Mar	July	=	Jul	November	=	Nov
April	=	Apr	August	=	Aug	December	=	Dec

3- In the absence of a precise date for an event or therapy that precedes the participant's inclusion into the study, a partial date may be recorded by recording "NK" in the fields that are unknown e.g. where the day and month are not clear, the following may be entered into the CRF:

0	0	Μ	A	R	2	0	0	9
DD MN		1MI	M		YY	ΥY		

Center Numbering:

Enter the center number (2 digits),

- Research Center of Air Force Specialized Hospital = 01
- Helwan University Hospital = 02

e.g.

Center Nº:	0	1
------------	---	---

Patient's	Patient's	Screening Visit
Nº:	Initials:	Initiation Visit

[figure not shown]
Patients' Numbering;

Enter Patients' Group (A, B, or C), then patient's number (from 001 to 297), e.g.

Patient's Nº	А	0	0	5	
--------------	---	---	---	---	--

No Carbon Required (NCR) CRF

The White original and the pink NCR CRF Will be retrieved by Minapharm personnel during his / her visit to the center. The yellow NCR card will be retained by investigator folder at the site

A study population of 297 patients with compensated chronic Liver Disease, will be randomized according to fibroscan in screening visit into 2 groups:

- Group 1: with non-cirrhosis, F0, F1 and F2.
- Group 2: with advanced fibrosis and cirrhosis, F3 and F4

Subjects will be randomized into the 3 treatment groups with a balanced ratio of 1:1:1

- Group A (Experimental group), will receive Ursoplus[®] capsules (UDCA 250mg & Silymarin 140mg) = 99 subjects
- Group B (Control group 1), will receive Ursofalk[®] capsules (UDCA 250mg) = 99 subjects
- Group C (Control group 2), will receive Placebo = 99 subjects

Patient's		
Initials:		

[figure not shown]
Child-Pugh Score Calculation:

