2 STUDY DESIGN

This is a Prospective, Multi center, open-label, randomized, control, Interventional, phase IV Study will be conducted in 2 sites in Egypt; the Research Center of Air Force Specialized Hospital and Helwan University Hospital to assess the efficacy & safety of Ursoplus® capsules (UDCA 250mg & Silymarin 140mg) versus UDCA alone versus Placebo among compensated Chronic Liver Disease Patients.

This study is a clinical trial that will enroll 297 patients, based on Vibration-controlled transient elastography in screening visit; subjects will be enrolled in 2 groups:

- Group 1: with non-cirrhosis, F0, F1 and F2.
- Group 2: with advanced fibrosis and cirrhosis, F3 and F4

Subjects in each group (1 or 2) will be treated with either:

- Ursoplus[®] capsules (group A),
- Ursofalk® capsules (UDCA 250mg); group B (control group 1):
- Or with Placebo, in group C (control group 2), using Stratified random sampling

Generated by Data Management department (DM) of the CRO (Nagy Research) for the 3 treatment groups with a ratio of 1: 1:1. Subjects who will be enrolled in this study will agree to the release of information and sign an informed consent. Subjects included in this study are enrolled for the collection of data that reflect the care they receive under routine clinical circumstances. All provided care should be according to protocol and the local standard of medical care.

The screening and enrollment period is planned to be 6 months. The total duration of the study/subject will be 6 months for treatment, follow-up, and End of Study visits

3 Inclusion and Exclusion Criteria:

3.1 Inclusion Criteria:

Subjects meeting all of the following criteria will be considered for enrollment in the study:

- 1. Male and female patients aged ≥ 18
- 2. Subjects with Compensated Chronic Liver Disease, defined as child 5-7.
- 3. Patients with mild disturbance of liver biochemical profile by one of the following criteria: (elevated Total Serum Bilirubin ≤ 3 mg/dl, or elevated Direct Serum Bilirubin ≤ 2 mg/dl, or elevated one or more of liver enzymes up to 3 times of the normal level).: (Alanine Transaminase (ALT), Aspartate Aminotransferase (AST), Alkaline Phosphatase (AIP) & Gamma Glutamyl Transpeptidase (GGT)).
- 4. Non-diabetic subjects and subjects with Controlled DM-type 1 and 2 patients, HbA1C up to 7.5%
- 5. Non-pregnant or lactating female patients

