11.3 Statistical methods

This section provides specifications for preparation of final Statistical Analysis Plan (SAP), which will be issued prior to database lock. Any differences compared to this statistical section should be identified and documented in final SAP. Analysis will be done using SPSS version 21.

Categorical variables will be presented by number and percentage. Chi square test (or its subsidiaries) will be used to determine the p value. P -value <0.05 is considered significant.

Numerical Parametric variables will be presented by mean, SD and range. Paired ttest will be used to determine p-value between before and after treatment. Repeated measure ANOVA will be used to calculate significant effect for each group independently from baseline to end of treatment. One-way ANOVA test will be used to show and determine p-value and significance between 3 treatment groups at each point.

Numerical Non-Parametric variables will be presented by Median and interquartile range. Wilcoxon Sign Rank test will be used to determine p-value between before and after treatment. Friedman test will be used to calculate significant effect for each group independently from baseline to end of treatment. Kruskal-Wallis test will be used to show and determine p-value and significance between 3 treatment groups at each point.

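### No between-arm analysis uses the hospital, though centre is recorded for every patient: a small, avoidable loss of precision, not a bias

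*SAP*

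**What the plan says.** - **Sites.** SAP section 2 states that the study "will be conducted in 2 sites in Egypt".
- **Allocation.** SAP section 8: "Randomization is done using Stratified random sampling according to Vibration-controlled transient elastography in screening visit". The two strata are F0–F2 and F3–F4. It continues: "Subjects will be randomized into the 3 treatment groups with a balanced ratio of 1:1:1", with 99 patients per arm and lists produced by the CRO's data management group. The CRF instructions in the Protocol file agree: patients "will be randomized according to fibroscan in screening visit into 2 groups". Neither text mentions centre or block size.
- **Analysis.** SAP 11.3, for parametric variables: "One-way ANOVA test will be used to show and determine p-value and significance between 3 treatment groups at each point". Kruskal-Wallis is the non-parametric counterpart and chi-square serves categorical variables. No covariate is named.
- **Reporting.** SAP 11.4 gives results overall and by fibrosis group. Shell Tables 1 to 14 have no centre row, column or adjustment.
- **Data.** The CRF instructions assign each hospital a two-digit code (01 or 02), so centre is known for every patient.

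**The concern.** Hospital is a baseline variable that may be related to laboratory and elastography outcomes. It is collected but used neither to balance the arms nor to analyse them. If outcomes differ between the hospitals, two things follow. Variation between hospitals stays in the residual and widens every between-arm confidence interval. In addition, the arms will by chance contain somewhat different shares of each hospital's patients, and the unadjusted difference in means carries that imbalance. What is at stake is precision, and how far a particular realised difference reflects hospital mix. It matters most for the smallest contrast, combination versus UDCA.

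**Working it through.** **Inputs from SAP section 7.** Effect size f = 0.2124591, alpha 0.05, three groups, 270 evaluable patients (90 per arm). The bilirubin changes in the cited study are +0.2 (placebo), −0.1 (UDCA) and −0.2 mg/dl (combination).

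**Assumptions (no figures in the documents).** Centre effect d = 0.25, 0.5 or 1.0 within-centre SD; one hospital recruits a share q = 50%, 30% or 20%.

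**1. The plan's own figure.** λ = f² × N = 0.2124591² × 270 = 12.187 and critical F(2, 267) = 3.0296, both as stated. The noncentral F gives power 0.885 against the stated 0.870. This 1.5-point gap does not affect what follows.

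**2. Scale.** The SD of the three changes is 0.170, and 0.170 / 0.2124591 = 0.80 mg/dl. This SD is back-solved, not stated. Combination versus placebo is then 0.4 / 0.8 = 0.5 SD, and combination versus UDCA 0.1 / 0.8 = 0.125 SD. The standard error of an arm difference is sqrt(2/90) = 0.149 SD.

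**3. Chance imbalance.** The SD of the difference in centre share between two arms is sqrt(2q(1−q)/n). For q = 0.5 and n = 90 this is 0.0745, so the 95% range is ±1.96 × 0.0745 = ±14.6 points. The shift in the arm difference is d × imbalance:

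| Hospital split | d = 0.25 | d = 0.5 | d = 1.0 |
|---|---|---|---|
| 50:50 | ±0.037 SD | ±0.073 SD | ±0.146 SD |
| 30:70 | ±0.033 SD | ±0.067 SD | ±0.134 SD |
| 20:80 | ±0.029 SD | ±0.058 SD | ±0.117 SD |

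Within one fibrosis group, assuming 45 per arm and 50:50, the imbalance range is ±20.7 points and the shifts are ±0.052, ±0.103 and ±0.207 SD. The standard error there rises too, to sqrt(2/45) = 0.211 SD, so the shift is no larger relative to it.

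**4. Operating characteristics.** Simulation of 4,000 trials per cell, N = 270, hospitals 50:50, omnibus test, within-centre SD as the unit, no fibrosis effect simulated:

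| d | Power, centre omitted | Power, centre in model | Type I error, centre omitted |
|---|---|---|---|
| 0 | 88.3% | 88.2% | 4.9% |
| 0.25 | 87.6% | 88.3% | 5.3% |
| 0.5 | 86.1% | 88.2% | 5.4% |
| 1.0 | 81.2% | 88.5% | 4.6% |

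Replacing f by f / sqrt(1 + d²/4) gives analytic power without centre of 87.9%, 86.4% and 80.0% for the three non-zero effects, in agreement. The mean unadjusted combination-versus-placebo difference stayed between −0.499 and −0.504 SD, against a true −0.5. There is no bias on average.

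**5. Stratifying the lists by centre without adjusting.** Power is 87.1%, 87.1% and 80.4% for d = 0.25, 0.5 and 1.0, so essentially nothing is recovered. Type I error falls to 2.4% at d = 1.0: the test becomes conservative. The benefit comes from the model term.

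**6. If 0.8 mg/dl is instead the total SD,** already including variation between hospitals, the planned power holds without centre, and adjusting raises it to 89.0%, 90.4% and 94.5%.

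**The case against.** The strongest reply is that stratifying by site is optional. Randomisation makes centre imbalance ordinary random error, and the standard error already allows for it. That is right, and it is why the point concerns precision.

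The endpoint also removes part of the mechanism. The primary analysis is percent change, in which a purely proportional assay difference cancels; a constant offset cancels in absolute change. This holds only in part: a constant offset does not cancel in percent change, case-mix differences need not cancel in either, and the comparisons of levels at each time point keep both kinds of offset.

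A reader might infer that imbalance could swamp the 0.1 mg/dl combination-versus-UDCA contrast. An assumed 0.3 mg/dl hospital difference in bilirubin change, times a 14.6-point imbalance, gives 0.044 mg/dl, or 44% of it. The documents do not support that as a headline. The 0.3 exceeds every within-arm change the plan quotes, and the imbalance is taken at its 95% limit. A typical imbalance of about 5 points gives 0.3 × 0.05 = 0.015 mg/dl. The standard error of the contrast, 0.149 × 0.8 = 0.12 mg/dl, already exceeds the contrast itself.

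Two limits on what can be seen also stand. Figure 1, the stratification diagram, is not shown, so a centre level there cannot be excluded, although the text around it names only elastography. And SAP 11.3 announces a final SAP, which could add the term.

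**Conclusion.** The point holds as a minor one. On the visible text, allocation is stratified by fibrosis group alone and no between-arm analysis uses the hospital. The loss is negligible if the centre effect is about 0.25 SD, about 2 points of power at 0.5 SD, and 7 to 8 points at 1 SD. These figures assume equal recruitment by the two hospitals and 90 evaluable patients per arm; unequal recruitment makes the chance imbalance smaller. The true centre effect cannot be judged from the documents.

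A reader might infer that the planned comparison is biased or that its false-positive rate is inflated. The calculations show neither. A reader might also infer that each hospital uses its own laboratory and elastography device. The documents do not say whether these are local or central, so a centre effect remains a possibility, not an established fact.

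**What to change.** In SAP 11.3, through the final SAP before database lock:

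1. Replace the one-way ANOVA for between-arm efficacy comparisons with a linear model containing treatment, centre and fibrosis group. For analyses within one fibrosis group, drop the fibrosis term and keep centre.
2. Kruskal-Wallis cannot take a centre term. Where it is planned, use a centre-stratified rank test (for example van Elteren for pairwise contrasts) or a rank-based model with centre.

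The cost is one degree of freedom for centre (267 to 266 residual degrees of freedom with 270 patients), one more for fibrosis group, and a few lines of text. No new data are needed, and the change remains possible after recruitment has started.

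Optionally, if allocation has not begun, SAP section 8 could specify four lists (two centres by two fibrosis groups) at 1:1:1. This is useful only together with item 1. Because the trial is open label, block sizes must be concealed or varied so that the next allocation at a site cannot be guessed. Arm totals could then depart slightly from 99 each. Balance at randomisation would also not carry over fully to the per-protocol set that SAP 11.2 uses for efficacy, which is a further reason to rely on the model.
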